#### CDC Recommendations

No recommendation can be made regarding the safety and effectiveness of weight-adjusted dosing of parenteral prophylactic antimicrobial agents for the prevention of surgical site infection (No recommendation/unresolved issue) (Key Question 1C).

No recommendation can be made regarding the safety and effectiveness of intraoperative redosing of parenteral prophylactic antimicrobial agents for the prevention of surgical site infection (No recommendation/unresolved issue) (Key Question 1D).

- Cochrane review of antibiotic prophylaxis for colorectal surgery

In 2014 a Cochrane review of antibiotic prophylaxis in colorectal surgery determined that aerobic cover, in addition to anaerobic cover, reduced surgical site infection (SSI) rates (RR 0.44, 95% C.I. 0.29 to 0.68) (Nelson 2014). This benefit obtained by addition of aerobic cover is the potential for surgical efficacy to be reduced if Enterobacteriaceae (aerobe) resistance impacts on the efficacy of antibiotic prophylaxis. No recommendations are made on antibiotic dosing.

- Meta-analysis of ceftriaxone vs other antibiotics for antibiotic prophylaxis.

Ceftriaxone, an antibiotic with a long half life, has been assessed in relation to other cephalosporins with shorter half lives and been found to be more effective. For abdominal surgery it is more effective, having an odds ratio of 0.5 (Woodfield 2009).

### **Brief description of proposed study**

We propose to randomise patients due to undergo colorectal surgery to standard antibiotic prophylaxis or an interventional antibiotic prophylaxis regimen and assess surgical site infection (SSI) rates. Standard antibiotic prophylaxis is a pre-operative injection of cefuroxime, repeated every 4 hours. The intervention regimen is a loading dose of cefuroxime followed by a continuous infusion of cefuroxime until the end of surgery. The intervention regimen dosing will be calculated using a patient's renal function. The intervention regimen will target a free serum drug concentration of 64mg/L. This serum level is 4x the MIC90 for colonising Enterobacteriaceae. The rationale for this dosing regimen is summarised below. The primary objective of the study is to reduce by 50% the rate of surgical site infections after colorectal surgery.

The rationale for this study design is based on the following rationale. An expert assessment is that  $ft > MIC$  is the measure most likely to be applicable to prophylaxis (Moine 2013). But as shown in table 2, this measure is not achieved by standard prophylaxis regimens. Neither do clinical data suggest this target achieves optimal prophylaxis. Therefore there is an opportunity to optimise antibiotic prophylaxis dosing. As the exposure response-relationship (pharmacodynamic target) is unknown we could either complete a number of studies exploring different relationships, or compare standard treatment to a single regimen which included a number of exposure-response relationships. The two most common exposure-response relationships are the CMAX/MIC ratio and the  $ft > MIC$ . And it has been reported that killing, as opposed to inhibition used in MIC values, is optimised by achieving 4 times an MIC value (Macgowan). An antibiotic prophylaxis regimen which achieved drug concentrations of 4xMIC for the duration of surgery would therefore achieves a high CMAX/MIC ratio, high  $T > MIC$ , and optimise bacterial killing. Therefore, standard dose antibiotic prophylaxis will be compared against a PD target dosed antibiotic prophylaxis regimen. The PD target will be a free serum antibiotic concentration of 4xMIC90 for Enterobacteriaceae against cefuroxime. Bolus-Continuous infusion of antibiotic prophylaxis will ensure there is continuous targeting of this drug level throughout the operation.

## **2 RATIONALE**

**Research question:** Does pharmacodynamic target (4x MIC90 free serum concentration) based continuous antibiotic dosing of antibiotic prophylaxis reduce the rate of surgical site infection after colorectal surgery when compared against standard antibiotic prophylaxis dosing regimens.

**Research hypothesis:** Pharmacodynamic target (4x MIC90 free serum concentration) based continuous antibiotic dosing of antibiotic prophylaxis reduces the rate of surgical site infections after colorectal surgery by 50% when compared against standard antibiotic prophylaxis dosing regimens.

### Importance of research question

Surgical site infections after colorectal surgery are an important post-operative complication.

- 78,000 patients annually undergo elective colorectal surgery in England (Hospital Episode Statistics 2014) with approximately 22% (12%) developing an SSI. 9000 patients undergo emergency surgery, with approximately 30% developing an SSI.
- SSIs after colorectal surgery have been associated with an increased hospital stay (Kirby 2015a)
- SSIs are recognised as a patient safety issue: The National Patient Safety website and the Patient Safety First campaign highlight that prevention of SSIs is an NHS patient safety priority.
- On average each SSI is treated with 8 days of antibiotics. Antibiotic consumption is associated with antibiotic resistance.
- It is recognised that antibiotic resistance threatens the viability of surgical procedures. Sally Davies, England's Chief Medical Officer, has said "antibiotic resistance could routinely result in deaths from minor surgery". If new antibiotics are developed they are unlikely to be used for routine prophylaxis. We must therefore do better with the antibiotics we currently have.
- The English National Point Prevalence Survey of HCAs identified 13.2% of antibiotics prescribed in hospital each day were for surgical prophylaxis. This is therefore an important area to dose correctly.

### Why closely related questions are not being answered

#### Weight based dosing/intra-operative re-dosing.

The CDC systematic review on the prevention of surgical site infections identified 10 key questions after consultation with expert sources. Five of these questions were related to antibiotic prophylaxis, three were answered with a recommendation, but two questions received no recommendation and were identified as an unresolved issue. These two questions relate to:

- 1- The safety and effectiveness of weight-adjusted dosing of parenteral prophylactic antimicrobial agents for the prevention of surgical site infection.
- 2- The safety and effectiveness of intraoperative redosing of parenteral prophylactic antimicrobial agents for the prevention of surgical site infection.

Both these questions are essentially asking if dosing of antibiotic prophylaxis can be optimised. The Colo-Pro study will address both these questions in a single study of optimised dosing of antibiotic prophylaxis. PK analysis has shown that weight is not an important variable in an optimised regimen, but renal function is. PD target dosing includes renal function within the dose calculation, which PK

analysis suggests is more important than weight, and the continuous infusion addresses the aim of re-dosing i.e. maintaining “therapeutic” drug levels through the operation.

### Individualised antibiotic prophylaxis

An individual’s antibiotic prophylaxis could be modified based on antibiotic resistance testing of colonising Enterobacteriaceae. The challenges to this approach are

- 1- Time delays involved in testing
- 2- No established or defined sensitive/resistance testing protocols. Sensitive resistance classifications used for treatment may not be relevant to the prophylaxis setting.
- 3- Logistics of individualising prophylaxis
- 4- Excludes emergency surgical patients
- 5- Excludes the possibility of reducing SSI rates in the majority of patients with sensitive Enterobacteriaceae (80%) who have a high rate of SSIs

Rapid molecular testing could be completed, as per the R-GNOSIS study, which is using a rapid molecular test. In the UK we have low rates of ESBL infections, and detection of a resistance mechanism may not be informative with regard the expression of the resistance mechanism. Despite the limitations of this approach it is a potential avenue of research. We would explore the testing aspects of this approach within the Colo-Pro study. Rectal swabs would be collected pre-operatively and various biomarkers with regard to colonising Enterobacteriaceae (Species, Concentration, Antimicrobial susceptibility testing) would be determined and related to outcomes. This will allow a greater understanding of resistance in the prophylaxis setting, and what the best test of resistance testing and individualising antibiotic prophylaxis would be.

### Alternative antibiotic choice

Another strategy to reducing SSI rates could be to compare alternative antibiotics. There are some new antibiotics e.g. tigecycline, and old antibiotics e.g. fosfomycin, that could be used for antibiotic prophylaxis. The use of these antibiotics could potentially help mitigate some of the impact of antibiotic resistance. They may not though be expected to reduce SSI rates for the majority of patients who have susceptible Enterobacteriaceae and so not answer questions identified by the CDC experts relating to weight based dosing and re-dosing. Nor the question set by this study of PD target driven dosing. Alternative antibiotics may also have limitations e.g. tigecycline has no activity against *Morganella* or *Proteus* spp. In settings of high resistance we think a strategy of alternative antibiotics should be explored and we would consider investigating it once more fundamental principles of antibiotic dosing for surgical prophylaxis have been established in the Colo-Pro study.

### Risk based approach to alternative regimens

Another strategy to avoid treating patients colonised with resistant Enterobacteriaceae with antibiotics they were resistant to would be to create an antibiotic resistance risk prediction rule. In our Leeds study (Kirby 2015b) there were no factors which predicted colonisation with a resistant Enterobacteriaceae.

### Non absorbable oral antibiotics

The Cochrane review of antibiotic prophylaxis in colorectal surgery asked if oral (PO) non absorbable oral antibiotics given in addition to intravenous (IV) antibiotics for antibiotic prophylaxis were able to

reduce SSI risk. It was reported that combining these two regimens reduced SSI rates (RR 0.56 [0.43, 0.74]) compared to IV therapy alone. These trials were carried out in an era of pre-operative bowel cleaning preparation. Pre-operative bowel preparation has not been associated with clinical benefit so is now not recommended, and it is not known if this will reduce the efficacy of non absorbable oral antibiotic prophylaxis. A number of trials in this meta-analysis were limited by including systemically absorbed PO antibiotics. In addition the PO regimens included regimens given for a number of days, which may increase the opportunity for selection of antibiotic resistance. There are large trials not included in the Cochrane review which do not show a benefit of oral antibiotic prophylaxis (Kobayashi 2007). There is therefore clearly clinical equipoise in this area and it is suggested research is carried out. We suggest this should be carried out after the IV antibiotics have been assessed for optimisation given the increased chance of resistance associated with more prolonged courses of antibiotics.

### Long half life antibiotics

See background section: Long half life antibiotics.

### **Available treatments and their limitations**

In the UK three regimens are commonly recommended for antibiotic prophylaxis:

- 1- Co-amoxiclav 1.2g IV
- 2- Cefuroxime 1.5g IV and Metronidazole 400mg IV
- 3- Amoxicillin 1g IV, Gentamicin (various doses), and Metronidazole 400mg IV

### There are a number of potential limitations to these treatments

- 1- Dosing is fixed. This may result in antibiotic drug levels which are lower than intended, with an increased risk of antibiotic prophylaxis failure.
- 2- Dosing is single dose, and the antibiotics have a short half-life, 1-2 hours. This can result in antibiotic drug levels which are lower than intended, with an increased risk of antibiotic prophylaxis failure.
- 3- The dosing of these antibiotics has not been optimised.
- 4- Antimicrobial resistance may be having an impact on the efficacy of prophylaxis
- 5- Increasing antibiotic MICs, even within the susceptible range, may be having an effect on the efficacy of prophylaxis.
- 6- If re-dosing is recommended, it is frequently forgotten by the surgical/anaesthetic team.

### The potential improvement of the Investigational Medicinal product (IMP) over the standard treatments is:

- 1- Dosing is varied based on renal function, ensuring targeted drug levels are more likely to be achieved increasing the chance of antibiotic prophylaxis success.
- 2- Dosing is continuous, avoiding the risk of low levels during the procedure.
- 3- The dosing achieves MIC serum levels equal to 4x MIC90 throughout the operation, a level which will potentially provide an optimised antibiotic prophylaxis regimen.
- 4- A continuous infusion will remove the need for a surgeon/anaesthetist to remember to provide recommended re-dosing during an operation.

### The minimum clinically important difference

From the patients perspective the receipt of antibiotic prophylaxis by single dose or continuous infusion is not important given they are anaesthetised for duration of antibiotic administration. And the dosing is not expected to increase the risk of side effects. Therefore any reduction in SSI rates will be acceptable to the patient. Though not expected, there are potential risks to patients e.g. increased risk of thrombophlebitis, vascular access related complications; larger overall doses of antibiotic may increase *C. difficile* risk and risk of antibiotic resistance. The alternative beta-lactam used in the UK for prophylaxis is co-amoxiclav. There is evidence that cefuroxime has a lower *C. difficile* infection risk than co-amoxiclav supporting the choice of cefuroxime (Slimings 2014).

The additional cost of a continuous infusion regimen is likely to be minimal for an individual patient. There will be no additional cost beyond those associated with the infusion equipment and additional antibiotic costs. These are likely to be small in relation to the cost of £5000 per SSI i.e. only a 1 or 2 percent reduction in SSI rates is likely to be cost effective.

The study will therefore not be powered based on a minimally clinically important difference but will consider expected reductions in SSI rates.

### Justification for the dosage regimen and treatment duration

Antibiotic prophylaxis at treatment doses is the most effective intervention for the prevention of SSIs. Despite this effective intervention a significant minority of patients, >10%, still suffer SSIs. Therefore, if it is possible to improve the efficacy of prophylaxis it is likely, given the limited benefits of other interventions aimed at reducing SSI rates, that this intervention would offer the most rewards in terms of reducing SSIs. To improve the efficacy of an antibiotic intervention it would be normal practice to design a dosing regimen using the known exposure-response relationship. An exposure-response relationship would define the most effective dosing regimen. Different exposure-response relationships have been identified in the treatment of infections. For example, aminoglycoside dosing is optimised by getting a high ratio of peak drug concentration/MIC. For beta-lactams the time the serum level is above the MIC is important. The exposure-response for antibiotics used for prophylaxis is unknown.

We have therefore decided to investigate if a pharmacodynamic (PD) target based dosing approach, with a single target that covers a number of different exposure-response relationships, is more effective than standard antibiotic dosing regimens. The use of a PD target, as opposed to simply giving higher doses, means that we address issues highlighted as being important. These include obesity and the need to maintain antibiotic drug levels throughout the duration of surgery. A PD target of a free serum drug concentration of 4 x MIC 90 value has been chosen as up to this level bacterial killing is reported to increase (MacGowan 2011). This level equates to 64mg/L for and cefuroxime, which is below a level of 100mg/L. It has been suggested that a level of <100mg/L is a safe beta-lactam target to aim for (Moriyama 2010). This level will potentially increase the killing of bacteria including those that are resistant (MIC>8mg/L). The PD target chosen, 4xMIC90, therefore addresses concerns that antibiotic resistance is impacting on the efficacy on standard dosing of antibiotic prophylaxis.

### Choice of control interventions:

Intravenous cefuroxime 1.5 grams pre-operatively, and repeated at 4 hours will be the standard treatment, in combination with intravenous metronidazole 500mg as a single pre-operative dose.

This equates to standard treatment.

## 2.1 Assessment and management of risk

Benefit analysis: The potential benefits from the IMP are a reduced SSI rate which is estimated to be in the order of a 50% reduction. SSIs are associated with increased length of hospital stay, increased cost and increased antibiotic consumption.

### Risk analysis

Beta-lactam antibiotics are generally very well tolerated. The most serious potential risk is anaphylaxis which is reported in 1-5/10,000 doses. As per usual clinical practise, patients will have their allergy status checked pre-operatively and those with a known relevant allergy excluded from the trial. For those included, we have no reason to believe that continuous infusion is any more likely to result in an allergic reaction than bolus dose. The risk above standard treatment with in this study protocol is the higher dose of cefuroxime required to achieve the target a serum level of 64mg/L for the duration of surgery (53% <3 hours, 95% < 6 hours). Cefuroxime levels above 64mg/L are surpassed after bolus administration of intravenous therapy. But due to cefuroxime's short half life (1.5 hours) these levels normally fall over the following hours. Continuous infusions of beta-lactam antibiotics, in order to achieve continuously targeted serum concentrations of up to 100mg/L, have been administered for days of treatment without reported adverse events (Moriyama 2010). Other beta-lactams e.g. piperacillin, are given at 4g in a single dose (repeated 8 hourly). Cefuroxime can be dosed at higher doses (higher dose 3g 8 hourly, vs standard dose 1.5 g 8 hourly) for meningitis. This suggests targeting cefuroxime serum levels of 64mg/L for up to 6 hours is unlikely to result in dose related adverse events. See section 8.6 for full details of the study intervention dosing regimen.

An assessment of adverse events associated with cefuroxime is provided in the products SPC:  
<https://www.medicines.org.uk/emc/medicine/16929>

**This study has been reviewed by the MHRA and assessed as not being a CTIMP.**

### Risk minimisation/management

- Administration of doses: Anaesthetists/Research staff will administer antibiotics. They will use a programmable infusion pump to dose according to the protocol.
- Intravenous antibiotics can cause phlebitis, therefore antibiotic administration recommendations will be that where possible a 14G cannula/largest possible is used for administering antibiotic into a large peripheral vein.

## 3 OBJECTIVES AND OUTCOME MEASURES/ENDPOINTS

### 3.1 Primary objective

To determine if pharmacodynamic target (4xMIC90 free serum concentrations) based continuous antibiotic dosing of antibiotic prophylaxis reduces the rate of surgical site infections after colorectal surgery when compared against standard antibiotic prophylaxis dosing regimens.

### 3.2 Secondary objectives

To determine if pharmacodynamic target (4xMIC90 free serum concentrations) based continuous antibiotic dosing of antibiotic prophylaxis reduces the rate of all in-patient infections after colorectal surgery when compared against standard antibiotic prophylaxis dosing regimens.

To determine if pharmacodynamic target (4xMIC90 free serum concentrations) based continuous antibiotic dosing of antibiotic prophylaxis reduces the in-patient consumption of antibiotics after colorectal surgery when compared against standard antibiotic prophylaxis dosing regimens.

To determine if pharmacodynamic target (4xMIC90 free serum concentrations) based continuous antibiotic dosing of antibiotic prophylaxis reduces the length of hospital stay after colorectal surgery when compared against standard antibiotic prophylaxis dosing regimens.

To determine if pharmacodynamic target (4xMIC90 free serum concentrations) based continuous antibiotic dosing of antibiotic prophylaxis reduces mortality after colorectal surgery when compared against standard antibiotic prophylaxis dosing regimens.)

To determine if pharmacodynamic target (4xMIC90 free serum concentrations) based continuous antibiotic dosing of antibiotic prophylaxis reduces anastomotic leak after colorectal surgery when compared against standard antibiotic prophylaxis dosing regimens.

To determine if pharmacodynamic target (4xMIC90 free serum concentrations) based continuous antibiotic dosing of antibiotic prophylaxis improves quality of life after colorectal surgery when compared against standard antibiotic prophylaxis dosing regimens.

To determine if pharmacodynamic target (4xMIC90 free serum concentrations) based continuous antibiotic dosing of antibiotic prophylaxis reduces the cost of healthcare treatment after colorectal surgery when compared against standard antibiotic prophylaxis dosing regimens.

To determine if pre-operative antibiotic resistance, as determined by antibiotic susceptibility testing of rectally colonising Enterobacteriaceae, is predictive of a patients risk of a post-operative surgical site infection.

To determine the exposure-response relationship for antibiotic prophylaxis in the prevention of surgical site infection prevention after colorectal surgery.

### 3.3 Outcome measures/endpoints

#### 3.4 Primary endpoint/outcome

Primary endpoint: Surgical site infection within 30 days of operation.

Endpoint aggregation by percent.

Timings of measurement: Day 5, Day 30.

#### Rationale for the choice of trial endpoint/outcome

The Centre for Disease Control's (CDCs) National Nosocomial Infections Surveillance (NNIS) criteria for defining SSIs, to be used in this study, have been widely applied to SSI research studies. Application of these criteria has been shown to differentiate the effectiveness of SSI interventions in a number of studies e.g. antibiotic prophylaxis and surgical skin preparation. Whilst these criteria do have some limitations, principally the application involves a subjective assessment of the wound, we have agreed access to a SSI assessment training package developed for the ROSSINI trial (NIHR RfPB funded) to help standardise SSI assessment.

#### 3.5 Secondary endpoints/outcomes

- All in-patient infections within 30 days of operation
- All in-patient antimicrobial consumption within 30 days of operation.
- Length of hospital stay after operation
- Mortality after operation at one year.
- Anastomotic leak within 30 days of operation
- Quality of life scores pre-operatively and at 30 days.
- Cost of healthcare treatments after operation at 30 days.

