
Secondary
	
To reduce the rate of all infections after colorectal surgery.
 
To reduce antimicrobial consumption after colorectal surgery
 
To reduce length of hospital stay after colorectal surgery
 
To reduce mortality after colorectal surgery
 
To reduce anastomotic leakage after colorectal surgery
 
To improve quality of life after colorectal surgery
 
To reduce the cost of healthcare treatment associated with colorectal surgery
 
To investigate if pre-operative antibiotic resistance, as determined by antibiotic susceptibility testing of rectally colonising Enterobacteriaceae, is predictive of a patients risk of a post-operative surgical site infection.
 
To investigate the exposure-response relationship for antibiotic prophylaxis in the prevention of surgical site infection prevention after colorectal surgery.
	
All infections within 30 days of operation.
 
Antimicrobial consumption within 30 days of operation.
 
Length of hospital stay after operation
 
Mortality after operation at one year.
 
Radiological or clinically diagnosed anastomotic leakage
 
Quality of life scores pre-operatively and post operatively at 30 days.
 
Cost of healthcare treatments after operation at 30 days.
 
See Table 5
 
See Table 5

Medicinal Product	Cefuroxime 1.5g powder for solution for injection or infusion
Formulation, Dose, Route of Administration	
Formulation
 
Cefuroxime: Each vial contains, as the active ingredient, cefuroxime sodium for injection 1578mg equivalent to 1500mg of cefuroxime respectively
 
Dose
 
Standard treatment
 
 
• 1.5 grams 4 hourly.
 
 
Intervention treatment:
 
 
• A maximum loading dose of cefuroxime 2332 mg
 
• A maximum hourly dose on continuous infusion of 1226 mg/hour. These doses will be administered for a maximum of 6 hours.
 
 
Route of administration
 
Intravenous

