## 11 DATA HANDLING

### 11.1 Data collection tools and source document identification

Data collection will be by paper case report forms (CRFs)

CRFs will be created to document

- Surgical history, including antibiotic prophylaxis and blood collection timings
- Day 5 surgical site infection assessment
- Post operative medical history including antibiotic consumption within 30 days of surgery, infection diagnoses and length of hospital stay
- End of study form including mortality data
- Quality of Life questionnaires (EQ5-D)
- Surgical site infection questionnaire.

Records of all participating patients (sufficient information to link records e.g., CRFs, hospital records and samples), all original signed informed consent forms and copies of the CRF pages will be kept.

Records will be stored in a locked room at the Old Medical School, Leeds General Infirmary, Leeds.

All research forms will be labelled with a patients study number.

To maximise data collection, telephone assessments and postal questionnaires will be used where patients are unable to attend in person for assessments.

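### Infections and antimicrobial use are 30-day outcomes in the trial summary but in-patient-only in sections 3.2 and 3.5; one definition is needed, and the in-patient one depends on discharge

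*Combined protocol and SAP*

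**What the plan says.** **Trial summary.** The secondary outcome measures include "All infections within 30 days of operation" and "Antimicrobial consumption within 30 days of operation". Neither is limited by setting. The summary also lists the objective "To reduce length of hospital stay after colorectal surgery".

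**Section 3.2.** The matching objectives ask whether the regimen "reduces the rate of all in-patient infections after colorectal surgery" and whether it "reduces the in-patient consumption of antibiotics after colorectal surgery".

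**Section 3.5.** The endpoint list has "All in-patient infections within 30 days of operation" and "All in-patient antimicrobial consumption within 30 days of operation". Length of stay appears in the same list.

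**Data collection.** In section 7.7, infections are assessed against standard definitions at Visit 3 and then every 72 hours while the patient is in hospital. Visit 5 (day 30 to 45, normally postal or telephone) takes an antibiotic history and a questionnaire on outpatient SSIs. Section 11.1 has the CRF record "antibiotic consumption within 30 days of surgery"; it lists infection diagnoses too, but gives them no explicit window. Section 9.3 monitors adverse events to day 30 and names SSIs and other infections among the expected ones. Appendix 4 schedules a notes review, including antibiotic prescribing, and an adverse-event assessment at 30 days.

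**Analysis.** Section 10.3.3 compares secondary outcomes as proportions, and section 10.5 plans no adjusted analysis.

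**The concern.** Two analysts who each follow the document faithfully could report different results for the same outcome, one from the summary and one from section 3.5.

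The choice between the definitions matters. Under the in-patient version, how long a patient is observed depends on when that patient leaves hospital. Discharge comes after randomisation, and the regimen is meant to bring it forward. The planned comparison of proportions makes no allowance for days in hospital, so a difference in stay between arms would feed directly into both counts.

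There is also a problem of nesting. The primary endpoint (section 3.4) is SSI within 30 days with no limit on setting, and Visit 5 collects outpatient SSIs for it. Under section 3.5 those SSIs would not count as in-patient infections, so an outcome meant to be broader than the primary could come out lower.

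The secondary conclusions on infection and antimicrobial use are at stake, as are the definitions a full trial might inherit. The primary endpoint is unaffected.

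**Working it through.** **Step 1: the definitions side by side.**

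| Place | Infections | Antimicrobial use |
|---|---|---|
| Trial summary | all, to day 30 | all, to day 30 |
| Section 3.2 | in-patient | in-patient |
| Section 3.5 | in-patient, within 30 days | in-patient, within 30 days |
| Section 11.1 (CRF) | diagnoses, no explicit window | to 30 days |

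The inconsistency needs no arithmetic. The plan states no figure on this point to reproduce, so what follows is an illustration of size.

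**Step 2: inputs.**
- From the documents: 90% of SSIs occur by day 14 (section 1), used as a proxy for the timing of all infections; 8 days of antibiotics per SSI (section 2); an SSI rate of 16.5% (section 10.1), or 30% for emergency surgery (section 2), used as stand-ins because no all-infection rate is given; 90 patients at 1:1, so about 45 per arm.
- Assumed: lengths of stay, because the documents give none; one fixed stay for everyone in an arm; the same true 30-day rate in both arms.

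**Step 3: share of infections with onset before discharge.** Take onset as exponential, truncated at day 30:

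F(t) = (1 − exp(−λt)) / (1 − exp(−30λ)).

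Setting F(14) = 0.90 gives λ = 0.159 per day. The in-patient rate is the 30-day rate × F(stay), so the apparent ratio between arms is F(shorter) / F(longer). It does not depend on the 30-day rate.

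| Stay (days) | F, shorter v longer | Apparent ratio | In-patient rate at 16.5% | Infections in 45 |
|---|---|---|---|---|
| 7 v 8 | 0.678 v 0.726 | 0.93 | 11.2% v 12.0% | 5.0 v 5.4 |
| 6 v 8 | 0.621 v 0.726 | 0.85 | 10.2% v 12.0% | 4.6 v 5.4 |
| 5 v 7 | 0.554 v 0.678 | 0.82 | 9.1% v 11.2% | 4.1 v 5.0 |

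At 16.5% the difference is below one patient per arm in every row. At 30% it is 0.7, 1.4 and 1.7 patients (for 6 v 8: 45 × (0.2179 − 0.1862) = 1.4).

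The chance of a nominally significant result favouring the shorter-stay arm (two-sided 5%, 45 per arm) is 3.3%, 4.5% and 5.1% at 16.5%, and 3.7%, 5.6% and 6.6% at 30%. With no distortion it would be 2.5%.

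**Step 4: antibiotic days in hospital per infection.** This is the mean of min(8, stay − onset day), floored at zero. Stays of 6, 7 and 8 days give 2.2, 2.8 and 3.5 days. The ratio is 0.61 for 6 v 8 and 0.80 for 7 v 8. Over the full 30 days the figure is 7.9 in both arms.

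**Step 5: nesting.** With a stay of 8 days, 1 − 0.726 = 27% of infections start after discharge. Of a 16.5% SSI rate, 16.5 − 12.0 = 4.5 percentage points would be missing from the in-patient count. Patients whose only infection was another in-patient one would offset some of this.

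**Step 6: the 30-day definition.** With equal true rates the ratio is 1.00 whatever the stay.

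**The case against.** A reader might infer that whichever arm goes home sooner will look better with no true benefit. The documents do not support that as a finding. Allocation is randomised. If the regimen affects neither infection nor stay, stays differ only by chance, which distorts a single comparison but has no systematic direction. The route to shorter stay that the protocol documents is fewer SSIs, and then the risk is exaggeration of a real effect. A route unrelated to infection, such as discharge decisions influenced by unblinded theatre staff, is possible, but section 7.4 blinds outcome assessors and staff not present at the operation.

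The illustration is also simplified. The protocol says SSIs prolong stay, so a patient infected in hospital would stay longer than the fixed stay assumed here, and more of the antibiotic course would be captured. Step 4 may therefore overstate the loss. SSI timing need not apply to respiratory or urinary infections.

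Two readings of the text also go too far. In-patient within 30 days need not end at first discharge, because it may include readmissions. The CRF's explicit 30-day window covers antibiotics, and section 11.1 does not clearly extend it to infection diagnoses.

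Finally, counting only in-patient infections can be defended on data quality: research staff apply standard definitions in hospital, while Visit 5 is usually remote and may fall as late as day 45. The protocol does not give this reason.

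All of this limits the size and certainty of any distortion. It does not remove the conflict between the definitions, the dependence of the in-patient window on discharge, or the omission of outpatient SSIs.

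**Conclusion.** The concern holds as an unreconciled definition of two secondary outcomes. The in-patient version is the weaker one, because its window depends on a post-randomisation event tied to another outcome and because it excludes events that the primary includes.

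Distortion is conditional on a difference in stay between arms. Its size is hypothetical: an apparent infection ratio of about 0.93 for 7 v 8 days and 0.85 for 6 v 8 days with no true effect, resting on assumed fixed stays and SSI-only timing. In a 90-patient pilot this amounts to about one patient or fewer per arm at a 16.5% rate, and between one and two for a 2-day difference at 30%. A spurious significant result is unlikely.

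Confidence is high for the inconsistency and limited for the amount of bias. Severity is minor to moderate.

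**What to change.** State one window and one setting for each outcome, identically in the summary, section 3.2 and section 3.5.

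- **Antimicrobial consumption:** adopt the summary's definition, all use to day 30 regardless of setting. The Visit 5 antibiotic history, the CRF and the 30-day notes review already provide for it, so this is a wording change.
- **Infections:** count to day 30 regardless of setting, including outpatient SSIs from Visit 5 and infections found in the day-30 notes and adverse-event review. Record onset dates, so that events reported at a Visit 5 held after day 30 can be placed inside or outside the window.
- **In-patient component:** report infections assessed in hospital to standard definitions separately, and say whether readmissions count.

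The cost is an edit to three places and a date field where one is lacking. A question at Visit 5 on infections other than SSIs would improve capture but is optional. The downside is that post-discharge infections other than SSIs will be less completely found and less well verified than in-patient ones. The separate in-patient report lets readers see how much of the total rests on them.
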